Moderate intensity respiratory muscle training (RMT) in ALS

NCT04224961

1. Protocol Title:

Moderate intensity respiratory muscle training (RMT) in ALS

2. Purpose of the Study:

The purpose of this study is to develop treatments that enhance or preserve respiratory strength and provide meaningful clinical improvements for people with ALS and other neurodegenerative diseases with respiratory muscle involvement. Our central hypothesis is that moderate intensity RMT, individually modulated based on RPE, is necessary to induce meaningful changes in respiratory muscle strength and other outcomes in subjects with ALS. Our objectives are to:

- 1) Determine the safety and feasibility of moderate intensity RMT in subjects with ALS targeting both the inspiratory and expiratory muscles using patient-reported ratings of perceived effort (RPE) to monitor and regulate intensity.
- 2) Make preliminary estimates of the effects of moderate intensity RMT on respiratory muscle strength, cough and swallowing, and quality of life.

We expect that moderate intensity RMT regulated with RPE (Foster et al., 2017) will be safe and well-tolerated across subjects, though the magnitude of response, based on changes in respiratory muscle strength, is expected to vary based on baseline respiratory muscle strength. That is, based on effect size calculations, we expect subjects with normal inspiratory muscle strength to demonstrate large to very large increases in respiratory muscle strength, while subjects with mild to moderate inspiratory muscle weakness (40-70% of predicted) will demonstrate a more modest response. Culmination of these objectives will provide pilot data for submission of a competitive NIH grant application to further study RMT in ALS in a larger group of subjects.

3. Background & Significance:

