Our laboratory has pioneered the use of moderate intensity RMT regimens to provide respiratory muscle resistance training and address progressive neuromuscular weakness (Jones et al, 2011, 2014, 2016). Counteracting respiratory muscle weakness with moderate intensity exercise offers a biologically plausible mechanism to target progressive inspiratory and expiratory muscle weakness in ALS. This research will be the first study of a comprehensive RMT program targeting both inspiratory muscle weakness with IMT and expiratory muscle weakness with EMT in individuals with ALS. We will also utilize a well-defined, moderate intensity RMT regimen and pioneer the use of patient-reported RPE to monitor and regulate intensity. We will use telehealth visits to collect measures of respiratory muscle strength (maximum inspiratory pressure [MIP], maximum expiratory pressure [MEP]) in order to 1) reduce the number of on-site visits required by participants and 2) improve our ability to collect repeated measures of our primary outcomes. We will continue to use the novel modifications, methods, and technologies we have developed to allow progressive, individualized, and calibrated RMT to be delivered across the range of human performance. These include our calibration methodology to ensure accurate, precise RMT pressure-threshold resistance (Jones et al., 2014, 2016) and the Inspiratory Adapter 150 (US Patent Pending) to allow use of expiratory-type devices for IMT (EMST 150; Aspire LLC) and expand the range of resistance.

The results of this study will be used to refine our RMT in ALS treatment regimen, select appropriate outcome measures, and develop the statistical analysis plan for use in a future NIH grant application to further study RMT in ALS in a larger group of subjects.

4. Design & Procedures:

Participants will be recruited from the Duke ALS Clinic or referred through CT.gov or outside hospitals. Twelve adults will participate in a single- subject A₁-B-A₂ study involving 4 visits to Duke over 24 weeks (see **Figure 1**). The 6 week delayed start period represented by A₁ will establish baseline status prior to initiation of RMT and A₂ will determine detraining effects over 6 weeks of RMT withdrawal. Participants will complete four 3-week cycles of progressive RMT during the B phase. We will measure

Moderate intensity respiratory muscle training (RMT) in ALS

NCT04224961

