Figure 1. Study Overview. MIP=maximum inspiratory pressure; MEP=maximum expiratory pressure; SNIP=sniff nasal inspiratory pressure; PCF=peak cough flow; ALSFRS=ALS Functional Rating Scale; EAT-10=Eating Assessment Tool-10; SF36=36-Item Short Form Survey; WHOQOL-BREF=World Health Organization Quality of Life Instrument-BREF; CES-R=Communicative Effectiveness Survey-Revised; RMT=respiratory muscle training (IMT+EMT); PRE=pretest visit; POS=posttest visit. *On-site visit. ^TTelehealth visit conducted via video conference. To minimize participant burden, M7 and M19 will be coordinated with ALS Clinic visits when possible.

Note: If M1, M7, M19, and M25 are completed remotely, the Peak Cough Flow will not be able to be measured.

Participants will be stratified into 2 groups based on baseline inspiratory muscle strength as determined by maximum inspiratory pressure (MIP): six participants with minimal to no respiratory weakness (i.e., MIP \geq 70% predicted) and six participants with mild to moderate inspiratory weakness (i.e., MIP 40-70% predicted).

The primary outcomes are MIP and MEP. Secondary outcomes include peak cough flow (PCF) and sniff nasal inspiratory pressure (SNIP). Exploratory outcomes include the Amyotrophic Lateral Sclerosis Functional Rating Scale (ALSFRS), Eating Assessment Tool – 10 Item (EAT-10), 36-Item Short Form Survey (SF36), World Health Organization Quality of Life-BREF (WHOQOL-BREF), and Communicative Effectiveness Survey-Revised (CES-R). Outcomes will be collected as shown in **Figure**

Moderate intensity respiratory muscle training (RMT) in ALS

NCT04224961

1 following established guidelines (ATS/ERS 2002; Evans & Whitelaw 2009, Tzani 2014; Kaminska et al 2017; Cedarbaum et al 1999; Belafsky et al 2008; Ware & Sherbourne 1992; Donovan 2013). Clinical spirometry data will be extracted from the participant's electronic medical record if available from a coinciding ALS Clinic visit that occurs +/- 5 days from the assessment visit.

5. Selection of Subjects:

Inclusion criteria:

- Age \geq 18 years
- Confirmed diagnosis of ALS
- Ability to follow directions for study participation
- Ability to successfully and independently complete RMT repetitions at a minimum pressure-threshold target equal to 30% of MIP or MEP
- Ability to complete telehealth visits using a smartphone or computer with video capabilities
- Ability to complete a home-RMT regimen

Exclusion criteria:

- MIP $<$ 40 cmH20
- Presence of a tracheostomy

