- Use of non-invasive or invasive ventilation when awake
- Participant or caregiver(s) inability to manipulate respiratory pressure meter, the RMT device, or calibration equipment for home training
- Inability to complete RMT repetitions successfully
- Concomitant neurologic or neurodegenerative conditions (e.g. stroke, dementia) or other serious conditions that would prevent meaningful study participation as determined at the discretion of the principal investigator
- Inability to give legally effective consent
- Inability to read and understand English

6. Subject Recruitment & Compensation:

Participants will be recruited from the multidisciplinary Duke ALS Clinic, an ALS Association Certified Center that actively follows approximately 400 patients per year. Potential subjects will be identified by review of medical records by study staff. Subjects may also be referred through CT.gov or outside hospitals. Potentially eligible subjects will then be approached by the study coordinator, PI, or other member of the study team trained in conducting the informed consent process. This may be done via Mychart, email, letter or phone. For non-Duke patients, records will be requested from the outside hospital to confirm eligibility. Patient opt-out status within Maestro Care will be reviewed before potential subjects are approached or communicated with. An opportunity to participate in the study will be offered to all DUHS patients or referrals who meet the inclusion/exclusion criteria, regardless of demographic group. Patients will be compensated \$25 upon completion of each visit at Duke for a total of \$100.

7. Consent Process:

The consent process will be conducted by the PI and study team designated to conduct the consent. The potential subject will have as much time as they need to decide if they would like to participate or not. The potential subject will be encouraged to take the consent home and discuss it with any family members if they wish. Once the study is explained, all questions have been answered, and the subject

Moderate intensity respiratory muscle training (RMT) in ALS

NCT04224961

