Two commercially available pressure-threshold RMT devices that utilize a spring-loaded flange to provide resistance against inspiration and expiration independent of respiratory flow rate will be used to provide the necessary range of resistance. Each participant will use two RMT devices, one for IMT and one for EMT. Device selection will be based on the target pressure-threshold resistance (see **Figure 2**). Participants requiring pressure-threshold resistance between 40 and 150 cm H₂O for expiratory training will use the EMST 150 device (Aspire, LLC). Expiratory resistance between 9 and 40 cm H₂O will be provided by the Threshold IMT device (Philips Respironics), achieved by placing the mouthpiece on the opposite end of the device. The Threshold IMT device will be used to provide pressure-threshold resistance between 9 and 40 cm H₂O for inspiratory training. The EMST 150 will also be used to provide pressure-threshold resistance between 41 and 150 cm H₂O for inspiratory training, using the Inspiratory Adapter 150 (Aspire, LLC).

Device	Inspiratory Training Range	Expiratory Training Range
EMST 150	41-150 cm H ₂ O (with Inspiratory Adaptor 150)	40-150 cm H ₂ O
Threshold IMT	9-40 cm H ₂ O	9-40 cm H ₂ O

Moderate intensity respiratory muscle training (RMT) in ALS

NCT04224961

Figure 2. Each participant will receive two RMT devices; device selection is dependent on target pressure-threshold resistance.

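### Does a MIP floor in cmH2O, set beside groups defined in % predicted, leave eligible people without a group?

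*Combined protocol and SAP*

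**What the plan says.** Section 4 (Design & Procedures) fixes the sample size: "Twelve adults will participate". Later in that section they are divided by baseline MIP into "six participants with minimal to no respiratory weakness", meaning 70% of predicted or more, and "six participants with mild to moderate inspiratory weakness (i.e., MIP 40-70% predicted". Section 2 uses the same lower band for its expected result: "subjects with mild to moderate inspiratory muscle weakness (40-70% of predicted) will demonstrate a more modest response".

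Section 5 (Selection of Subjects) has one MIP limit, the exclusion of anyone below 40 cmH2O. Its other strength criterion is the ability to train "at a minimum pressure-threshold target equal to 30% of MIP or MEP". That is relative to the person's own pressures, so it sets no limit in percent of predicted. No listed criterion uses percent of predicted.

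Section 6 says that participation "will be offered to all DUHS patients or referrals who meet the inclusion/exclusion criteria", and the sentence goes on to say that demographic group plays no part.

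Section 4 says outcomes are collected "following established guidelines" and cites sources, but does not say which equation supplies the predicted value.

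Section 12 plans descriptive statistics, visual analysis of the raw MIP and MEP series, and a single-subject d. It contains no comparison of the two groups.

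**The concern.** The number 40 appears as a lower limit on two different scales. One governs entry (cmH2O) and the other governs group membership (percent of predicted). They are the same limit only for a person whose predicted MIP is 100 cmH2O. For anyone with a higher predicted value, entry is wider than the groups, and a candidate could satisfy Section 5 and belong to neither group. For anyone with a lower predicted value, the absolute floor removes part of the 40-70% band.

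Three things would be at stake if this were a real hole: how staff screen a candidate who falls between the limits, how the two groups of six are filled, and how response is described by baseline strength, which is the contrast that Section 2 anticipates. With six per group, one misplaced person is a sixth of a group. Two smaller points add to the impression of looseness: a MIP of exactly 70% of predicted is literally in both ranges, and group assignment depends on a prediction equation that the protocol does not name.

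**Working it through.** **The plan's own figure.** The two quotas give 6 + 6 = 12, which matches the stated total. There is no power calculation to reproduce.

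**The gap.** Let P be a person's predicted MIP in cmH2O. The documents give no value of P, so it is assumed here to lie between 70 and 130.

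- Passes the Section 5 floor: MIP ≥ 40.
- Belongs to one of the Section 4 groups: MIP ≥ 0.40 × P.
- Passes the floor but fits no group: 40 ≤ MIP < 0.40 × P. This is possible only if 0.40 × P > 40, that is, P > 100.

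| Assumed P | 0.40 × P (cmH2O) | 40 cmH2O as % of P | Consequence |
|---|---|---|---|
| 70 | 28 | 57.1% | weaker group spans 57.1-70% |
| 80 | 32 | 50.0% | weaker group spans 50-70% |
| 90 | 36 | 44.4% | weaker group spans 44.4-70% |
| 100 | 40 | 40.0% | limits agree |
| 110 | 44 | 36.4% | no group for MIP 40 to <44 |
| 120 | 48 | 33.3% | no group for MIP 40 to <48 |
| 130 | 52 | 30.8% | no group for MIP 40 to <52 |

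Example: 45 / 120 = 37.5%, which is above the floor and below both groups. So the mismatch exists, on condition that P exceeds 100. In the rows below 100 the group label remains true of every member. Only the range actually studied is narrower.

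**Is there a place for such a person?** Section 4 gives numerical limits for both groups and a quota for each, and the quotas account for all twelve places. The number of places below 40% of predicted is 12 − 6 − 6 = 0.

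**Does group membership enter the analysis?** Section 12 defines d as (second mean − first mean) / SD of the first assessment, all within one person. The group label does not appear. Nor does the prediction equation: with P fixed for a person, re-expressing MIP as a fraction of P divides the numerator and the denominator by the same P, so d is identical on either scale.

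**Are two scales a mistake in themselves?** Section 9 gives the Threshold IMT device an inspiratory range of 9-40 cmH2O and a minimum training load of 30% of MIP. At the absolute floor, 0.30 × 40 = 12 cmH2O, inside that range. If the only floor were 40% of predicted, the corresponding load would be 0.30 × 0.40 × P = 0.12 × P, which is below 9 whenever P < 75 (at P = 70 it is 8.4). An absolute entry limit can therefore do a job that a percent-of-predicted band does not. The protocol does not give its reason for the floor. The calculation shows only that two scales can reasonably coexist.

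**The case for a change.** The strongest case for a change is that Section 5 is the section that decides who enters, and it never mentions percent of predicted. Section 4 speaks of stratifying participants, which reads as classifying people already enrolled and not as a screening rule. Section 6 ties the offer of participation to the Section 5 criteria. Someone who confirms eligibility from medical records and works from Section 5 alone could enrol a person for whom the protocol has no group and Section 2 has no expected response. Since the pilot is meant to inform a later grant application, it should be clear who was studied, and an unnamed equation means that group assignment cannot be reproduced from the protocol text alone.

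Part of this stands. The lower limit is in the wrong place for a reader of Section 5, the 70% boundary is written loosely, and no equation is named.

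The rest carries less weight. The Section 6 sentence is about demographic fairness. With about 400 patients followed per year and twelve places, it cannot mean that meeting the criteria guarantees entry. The 70% boundary has a natural reading, because one group carries an explicit greater-than-or-equal sign and the other is an ordinary range. On the equation, Section 4 cites a statement on respiratory muscle testing and a paper on mouth pressures in adults. Whether either settles the reference values cannot be seen from the documents, so the supportable statement is only that the protocol names none. And if a person below 40% of predicted were enrolled, the visual analysis and d for that person would be as valid as for anyone else. Only the group label in the write-up would need a sentence of explanation.

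**Conclusion.** The two lower limits do differ, and the arithmetic is right: if a candidate's predicted MIP exceeds 100 cmH2O, that person can pass Section 5 and fit neither group. That condition is an assumption, since the documents give no predicted values, and the number affected may be zero.

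This is a drafting inconsistency, and no change to the plan follows. The 40% limit is misplaced but not absent, and the quotas leave no place below it. No planned analysis compares the groups, and every single-subject d is the same whatever the group label or prediction equation. Cross-referencing the group limits in Section 5, putting exactly 70% in the upper group, naming the equation and listing baseline MIP in both units would only record what staff and analysts would do anyway. The conclusion rests on Section 12 as it stands. A formal comparison between the two groups would make the boundaries and the equation matter more.

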MIP and MEP weekly. To reduce participant burden and enhance our ability to obtain repeated measures, we will have the ability to obtain measurements of MIP and MEP during web-based telehealth visits.

Participants will complete a full assessment during the first study visit (M1), which may be performed in person or remotely via a web-based session, and receive training/instruction for obtaining MIP and MEP measurements at home with a portable, battery-powered digital pressure gauge manometer (MicroRPM Pressure Meter; Micro Direct). Prior to the pretest visit, participants who opt for remote visits will be mailed instructions for the home-based RMT regimen and the devices as well as a written treatment log. The pretest visit (M7) will include a full assessment after which RMT will commence. During the B phase, participants will complete 12-weeks of moderate intensity RMT, divided into four 3-week cycles, and participate in weekly web-based RMT therapy visits (M8-M18). Posttest assessment (M19) will occur immediately following completion of the 12-week RMT regimen. We will measure MIP and MEP during RMT withdrawal via web-based telehealth visits (M20-24). Following the fourth and final full assessment visit (M25), participants will return all equipment and will be offered the opportunity to initiate a clinical RMT regimen and receive follow-up care by Speech Pathology during future ALS Clinic visits.

Week	A1 (6 weeks)						B (12 weeks)												A2 (6 weeks)							
	0	1	2	3	4	5	6	7	8	9	10	11	12	13	14	15	16	17	18	19	20	21	22	23	24	
Measurement	M 1*	M 2 ^T	M 3 ^T	M 4 ^T	M 5 ^T	M 6 ^T	M 7*	M 8 ^T	M 9 ^T	M 10 ^T	M 11 ^T	M 12 ^T	M 13 ^T	M 14 ^T	M 15 ^T	M 16 ^T	M 17 ^T	M 18 ^T	M 19*	M 20 ^T	M 21 ^T	M 22 ^T	M 23 ^T	M 24 ^T	M 25*	
MIP	X	X	X	X	X	X	X	X	X	X	X	X	X	X	X	X	X	X	X	X	X	X	X	X	X	
MEP	X	X	X	X	X	X	X	X	X	X	X	X	X	X	X	X	X	X	X	X	X	X	X	X	X	
SNIP	X						X													X						X
PCF	X						X													X						X
ALSFRS	X						X													X						X
EAT-10	X						X													X						X
SF36	X						X													X						X
WHOQOL-BREF	X						X													X						X
CES-R	X						X													X						X
RMT							X	X	X	X	X	X	X	X	X	X	X	X	X	X	X	X	X	X	X	
	PRE						POS																			
	RMT Cycle 1						RMT Cycle 2						RMT Cycle 3						RMT Cycle 4							

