Participants will be asked to keep a paper log documenting the number of repetitions they complete each day as well as RPE and any pain they experience associated with home RMT.

See **Figure 4** and **Figure 5** for a detailed treatment decision tree and sequential list of treatment activities for each study visit.

10. Risk/Benefit Assessment:

Research participation is expected to be safe and well-tolerated based on our prior research using moderate intensity RMT in late-onset Pompe disease (Jones et al, 2011, 2014, 2016) and the relevant research in the ALS literature (Cheah et al., 2009; Pinto et al., 2012; Plowman et al., 2016). Multiple elements of our study design have been included to ensure rigorous safety monitoring and minimize risk including:

- Individualized, stepwise pressure-threshold resistance based on each subject's respiratory muscle strength and RPE;
- Weekly contact with the RMT clinician during the 12-week training period to foster adherence and assess for any negative side effects;
- A predetermined algorithm for modulating RMT intensity to ensure participant safety;
- Use of an experienced RMT clinician to conduct the RMT program with training and oversight by the PI;
- Calibration of RMT devices to ensure precise and accurate pressure-threshold resistance.

11. Costs to the Subject:

There are no costs to subjects to participate in this study.

12. Data Analysis & Statistical Considerations:

Descriptive statistics will be provided for all outcomes. Primary outcome measures of MIP and MEP will be analyzed using visual analysis of raw data in graphical format using the method described by Land and Gast (2014). Magnitude of change for our primary outcome measures will be determined using

Moderate intensity respiratory muscle training (RMT) in ALS

NCT04224961

Cohen's measure of effect size (d) as defined by the first equation for single-subject d provided by Busk and Serlin (1992). Simply stated, d is obtained by subtracting the mean of the first assessment from the mean of the second assessment, divided by the standard deviation of the first assessment. Effect size calculations will be determined to compare results from baseline (M0-M5) to withdrawal (M19-M24) and pretest (M7) to posttest (M18). We will use conservative interpretation guidelines for effect size calculations in which $d < 0.6$ is negligible, $d \geq 0.6$ modest, $d \geq 1.0$ large, and $d \geq 2.0$ very large.

13. Data & Safety Monitoring:

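### Section 12 scales the pretest-to-posttest d by the SD of a single visit, labels visits in a way no one numbering fits, and plans no effect size for detraining

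*Combined protocol and SAP*

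**What the plan says.** For MIP and MEP, Section 12 of the combined protocol and SAP plans two things besides descriptive statistics. The raw data "will be analyzed using visual analysis of raw data in graphical format", and the size of change is given by a single-subject d: second mean minus first mean, "divided by the standard deviation of the first assessment". Two comparisons are named: "baseline (M0-M5) to withdrawal (M19-M24") and "pretest (M7) to posttest (M18"). Values below 0.6 are read as negligible, from 0.6 as modest, from 1.0 as large and from 2.0 as very large.

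Section 4 and Figure 1 set the schedule. Visits run weekly from M1 (week 0) to M25 (week 24). For the start of training: "The pretest visit (M7) will include a full assessment after which RMT will commence". For its end: "Posttest assessment (M19) will occur immediately following completion of the 12-week RMT regimen". For the last phase: "We will measure MIP and MEP during RMT withdrawal via web-based telehealth visits (M20-24"), followed by a final full assessment at M25. Section 4 gives phase A2 the purpose of determining detraining effects. Section 6 of the outline (the outcomes text under Section 4) refers measurement procedures to cited guidelines; the number of efforts per visit, and which value represents the visit, are not stated.

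**The concern.** Three things do not fit together.

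- **Denominator.** In the pretest-to-posttest comparison the first assessment is one visit. Its SD either cannot be computed or describes effort-to-effort scatter on one day. The other planned d is divided by the scatter of weekly values. The same bands are then applied to two different scales.
- **Labels.** Section 12 names visits that do not exist or that belong to another phase in the schedule, so two analysts could use different visits.
- **Detraining.** The only d that uses A2 compares it with baseline, which measures what was retained, not what was lost after stopping.

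This matters because Section 2 states the expected result in the language of these bands (large to very large with normal inspiratory strength, more modest with weakness). Section 3 says the results will guide the choice of outcomes and the analysis plan for a later, larger study.

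**Working it through.** The plan gives no sample-size, power or precision figure to reproduce.

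**1. Labels (no assumptions).** Figure 1 maps week *w* to visit M(*w*+1).

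| Section 12 label | Read as visit number | Read as week number |
|---|---|---|
| M0–M5, baseline | no M0; M6 dropped | weeks 0–5 = M1–M6: fits |
| M7, pretest | week 6: fits | week 7 = M8, one week into training |
| M18, posttest | week 17, a training visit | week 18 = M19: fits |
| M19–M24, withdrawal | includes posttest, omits M25 | weeks 19–24 = M20–M25: fits |

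No single numbering fits all four. Consequences of the visit-number reading:

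- Section 9 prescribes 125 + 250 + 375 = 750 repetitions per muscle group per cycle, and 4 × 750 = 3000, matching the stated total. M18 precedes the last training week, so 375 + 375 = 750 of 6000 repetitions (12.5%) are still to come.
- M19–M24 lie 0 to 5 weeks after training ends (mean 2.5). M20–M25 lie 1 to 6 weeks after (mean 3.5).

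**2. Denominator with one value at M7.** The sample SD divides by n − 1 = 0, so d is undefined.

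**3. Denominator with repeated efforts at M7.** All inputs are assumptions: week-to-week SD 5 cmH2O; *r* = within-visit SD / week-to-week SD, from 0.25 to 2; *k* = 3 or 5 efforts, averaged within the visit; independent normal errors; no disease trend. Median d for a true gain of 5 cmH2O from M7 to M19, by simulation:

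| *r*, *k* | M7 SD | SD of M1–M6 |
|---|---|---|
| 0.25, 3 | 4.6 | 1.04 |
| 0.5, 3 | 2.3 | 1.01 |
| 1, 3 | 1.1 | 0.91 |
| 2, 3 | 0.6 | 0.69 |
| 2, 5 | 0.5 | 0.79 |

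With the M7 SD, the same true gain runs from negligible to very large, depending on effort repeatability. With the A1-series SD it stays at about 0.7 to 1.1 (1.07 is the top if M7 is added to the series).

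**4. Chance labels with no true change (one-sided).** With the M7 SD, d = √(2(1/*r*² + 1/*k*)) × *t* on *k* − 1 df. With the M1–M6 SD and single visits, d = √2 × *t* on 5 df. For the planned six-against-six comparison, d = √(1/6 + 1/6) × *t* on 5 df.

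| Comparison | P(d ≥ 1.0) | P(d ≥ 2.0) |
|---|---|---|
| M7 v M19, M7 SD, *r* = 0.25, *k* = 3 | 44% | 38% |
| M7 v M19, M7 SD, *r* = 1, *k* = 5 | 28% | 13% |
| M7 v M19, M7 SD, *r* = 2, *k* = 5 | 18% | 5% |
| M7 v M19, M1–M6 SD | 26% | 11% |
| Six A1 visits v six A2 visits | 7% | 0.9% |

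The M1–M6 SD lies inside the range given by the M7 SD. Changing the denominator fixes the scale; it does not by itself reliably lower chance labels, because each mean is still one visit.

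**5. Detraining.** Take, for illustration, baseline 60, posttest 75 and SD 5.

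| A2 mean | Baseline-to-A2 d | Posttest-to-A2 change in SDs |
|---|---|---|
| 60 | 0 | (60 − 75)/5 = −3.0 |
| 67 | (67 − 60)/5 = 1.4 | (67 − 75)/5 = −1.6 |
| 75 | (75 − 60)/5 = 3.0 | 0 |

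A baseline-to-A2 d of 0 could mean a gain fully lost or no gain at all.

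**The case against.** - **The formula implies several values.** Section 12 speaks of the mean of an assessment and paraphrases a cited equation, with effort procedures left to cited guidelines. This makes the undefined SD the less likely reading. It does not rescue the scale, since the SD is then a same-day one. A between-participant SD at M7 would be computable, but the text specifies a single-subject d.
- **The denominator does not drive false labels.** This stands. A reader might infer that the M7 SD is what produces large labels by chance; at *r* = 2 and *k* = 5 it produces fewer than the A1-series SD.
- **The labels are probably a slip.** Each carries a phase word, and three of the four are correct as week numbers. The intended visits can be guessed, and the 12.5% and the shift in time off training arise only if the labels are followed as visit numbers. An analysis section should still not need a guess.
- **Detraining is not ignored.** A reader might infer that A2 or the training effect goes unanalysed. It does not: the M7-to-posttest d spans training, and weekly A2 values enter the visual analysis and descriptive statistics. Only an effect size for loss after training is missing.
- **Calling the bands conservative.** The plan says: "We will use conservative interpretation guidelines for effect size calculations". A reader might take the chance rates to disprove this. The word describes the cut-offs, not an error rate, so this is a matter of preference.
- **Averaging all training visits would be steadier.** It would, but it is a different estimand. A linear rise to +10 at M19 averages 10 × (1 + … + 12)/(12 × 12) = 5.4, so at SD 5 it reads 1.1 instead of 2.0.

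**Conclusion.** Wrong as written, with limited impact. The label conflict, the single-visit denominator and the absence of a d from end of training to withdrawal follow from the text and need no assumed numbers. The size of the scale problem (median d of about 0.5 to 4.5, against about 0.7 to 1.1, for the same true +5 cmH2O) rests wholly on the assumed SDs, SD ratios and effort counts. The high end needs efforts that repeat much more closely within a day than visits do between weeks; at *r* = 1 the two denominators nearly agree.

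A smaller point also holds: read literally, any value below 0.6 is negligible, which includes a large loss. The sign and the graphs would show the loss, but the label would not.

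None of this undermines the study's main purpose. It is a 12-person descriptive pilot, and no test or decision rule depends on d.

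**What to change.** Amend Section 12 as follows.

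1. Correct the labels to the schedule: baseline M1–M6, pretest M7, posttest M19, withdrawal M20–M25.
2. Use the SD of the weekly M1–M6 values as the denominator of every d. State the number of efforts per visit and which value represents the visit.
3. Keep M7 to M19 on that denominator, with the raw change in cmH2O beside it. Add a d from end of training (M19, or the mean of M17–M19) to M20–M25 on the same denominator. Label A1 against A2 as net retained change.
4. Report the sign, so that a loss is not labelled negligible.

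An M8–M19 average against baseline is at most an optional supplement, because it dilutes a gradual gain.

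The cost is wording and light programming; the weekly data are already scheduled. Some labels may become less favourable. Single-visit and detraining values stay noisy: with no change, the M17–M19 to M20–M25 d is √(1/3 + 1/6) × *t* on 5 df and passes 0.6 in about 22%, with −0.6 equally often. Using M19 alone, √(1 + 1/6) × *t* on 5 df, passes 0.6 in about 30%.
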